2.3.2 CRITERIA FOR DISCONTINUING

Nursing home/hospital level:

- (1) If the institution no longer wants to participate,
- (2) Any circumstance that makes it impossible or irresponsible to continue study at the respective institution

Resident/patient level:

- (1) If a participant or its legal representative withdraws its consent,
- (2) Adverse events (AEs) that, in the judgment of study personnel, interfere with further participation in the trial,
- (3) Serious adverse events (SEAs),
- (4) Incidents that, in the judgment of study personnel, interfere with further trial participation,
- (5) Serious incidents,
- (6) The occurrence of a medical condition which is incompatible with continued trial participation.

These include, for example:

- a. Mycotic or bacterial inflammation, or other skin conditions in the study area that require topical (drug) treatment of the skin area with other products,
 - b. The development of a category II, III, IV pressure ulcer, or an unstageable pressure ulcer, or a suspected deep tissue injury (DTI)
- (7) If participants are permanently transferred outside the study site
 - (8) In the intervention groups: missing application of study products for more than 72 hours
 - (9) More than three missing study visits

An "adverse event" or "serious adverse event" is in accordance with the definitions of Regulation (EU) 2017/745 (MDR) as defined in Article 2(57) and (58). An "incident" or "serious incident" is in accordance with the definitions of Regulation (EU) 2017/745 (MDR) as defined in Article 2(64) and (65).

For the whole trial:

- (1) If the ethics committee withdraws the ethics approval
- (2) If after 8 months of recruitment less than $n = 60$ participants have been included
- (3) The CTAB unanimously decides after 8 months that study continuation is not suitable to answer the research questions.

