2.1 Definitions

Intention-to-treat/Full analysis population

The full analysis set (FAS) contains all participants that met the inclusion criteria and were randomized, irrespective of possible protocol deviations, discontinuation of the study treatment or withdrawal from the study by the subject. Study participants will be categorized according to the intended treatment. As only exception, the following reasons cause an exclusion of participants from the full analysis set: (I) No treatment was applied at all or (II) there are no data available after the subject's randomization. Subjects excluded from the full analysis set will be mentioned in the study report and reasons for exclusion will be documented per group. In case of consent withdrawal, all subject's data collected until this time point will remain part of the study database and may not be removed.

Per protocol population

The per protocol (PP) set is defined as follows: (I) Participants that completed the study without major protocol deviations or violations (i. e. wrong product/incorrect application, missing application for more than 72 h, more than three missing study visits, inclusion/exclusion criteria not met) and (II) terminated the study regularly (study participation of at least 7 consecutive days).

For all subjects included in the full analysis set but not in the PP set, the reason for exclusion will be stated in the study report per group.

Safety analysis set

The safety population comprises all patients. Due to blinding, it doesn't matter whether they received one dose of the product or not.

Nr.	Inclusion criteria	Variable name	Comment
1	Geriatric patients or residents (≥ 65 years) staying/living in one of the participating institutions	sc_0080, sc_0091	sc_0091 for age; see sc_0020 at mnppid_visit for detailed info
2	Being incontinent of urine and stool	sc_0100	
3	Expected minimum length of stay of 14 days	sc_0110	
4	Intact skin with no clinical signs of IAD or intact skin with early clinical signs of IAD but without clinical signs of infection (GLOBIAD category 1 A)	sc_0121	Check sc_0122 for IAD category
5	Written informed consent	sc_0130	
Nr.	Exclusion criteria	Variable name	Comment/Analysis
1	Residents/patients at the end of life	sc_0140	
2	Residents/Patients with skin loss due to IAD (GLOBIAD category 2 A) and/or signs of clinical infection in the IAD area (GLOBIAD category 1 B or 2 B)	sc_0150	

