2.2 Application

The primary efficacy analysis will be done using the FAS including estimated values from multiple imputations for missing values (ITT framework). Participants that die, discontinue participation or leave the institution during the study period will be analyzed until that time point (early termination).

An additional analysis of the primary efficacy variable in the PP analysis set will be used as sensitivity analysis. The safety analysis includes calculation of frequencies and rates of adverse and serious adverse events in the safety analysis set.

As the ITT analysis is intended to preserve the original randomization and to avoid potential bias due to exclusion, the PP analysis aims to analyze the possible effects of the intervention administered under optimal conditions. Therefore, both analyzes are a necessary component to determine the feasibility of the applied procedures as well as possible effects of the intervention. Especially with regard to planning of a subsequent confirmatory trial

[figure not shown]
3 Trial centres

The study was conducted in geriatric hospitals/geriatric wards (acute care setting) of participating hospitals and in institutional long-term care facilities (nursing home setting) of the federal state of Berlin, Germany with a recruitment of n = 220 patients. Of these, 25 subjects were enrolled from acute care settings (14 EGZB; 11 Charité-ITS) and 195 subjects were recruited across 18 different nursing homes.

Nr	Participating ward	Number of patients (n)
Geriatric hospitals		
1	EGZB	14
2	Charité intern ITS	11
Nursing homes		
1	NH-01	11
2	NH-02	19
3	NH-03	5
4	NH-04	19
5	NH-05	17
6	NH-06	10
7	NH-07	6
8	NH-08	9
9	NH-09	7
10	NH-10	19
11	NH-11	4
12	NH-12	25
13	NH-13	8
14	NH-14	7
15	NH-15	3
16	NH-16	3
17	NH-17	13
18	NH-18	10

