4.1 Demography and baseline characteristics

Demographic information (e. g. age, sex, care level), incontinence type according to medical records, medical information (e. g. relevant main medical diagnoses and relevant regular medication) and further care specific data is collected for all participants.

Characteristic	eCRF table	Variable name	Type	Scale	Comment/Analysis
Patient-ID		mnpaid			
Visit Number		mnpvismo			
	mnppid_random				Randomization information (strata)
arm		rd_0050	cat	1-A 2-B 3-C	Blinded (label permuted)
	mnppid_visit				Visit information
Visit performed?		visit_0011	Cat.		
Date of visit		visit_0012	Date		
Reason for no visit		visit_0013	Char.		
Setting		sc_0020	Cat.	1-Nursing home (NH) 2-Geriatric Hospital (GH)	Important: mnppid_visit; not mnppid_screening! =>rename setting_sc_0020
	mnppid_completion				
Date of study termination		sc_0010	Date		For “time under study” Take diff(sc_0010,visit_0012==Day0)
Did the subject complete the study regularly?		sc_0021	cat	1-Yes, completion of end of study visit on Day 14 2-Yes, but before end of study visit on Day 14 0-No	Reasons for 0 might be withdrawal before randomization or screening failure
Reasons for early termination		Sc_0031 to Sc_0038			Consider sc_003x_txt Except for 0031,0032,0037

Characteristic	eCRF table	Variable name	Type	Scale	Comment/Analysis
	mnppid_demo				Demography & Medical Data
A Demography					
Age		dm_0020	Cont.	years	Mean (sd)
Sex		dm_0030	cat	1-male 2-female	n (%)
Body height		dm_0041	Cont.	cm	Mean (sd)
Body weight		dm_0051	Cont.	kg	Mean (sd)
BMI		dm_0060	cont	Score	Mean (sd)
Care level		dm_0070	cat	0-none 1-1 2-2 3-3 4-4 5-5 -1-Unknown	n (%)
Smoking status		dm_0080	cat	1-Smoker 2-Non-Smoker -1-Unknown	n (%)
Skin type		dm_0090	cat	1-I 2-II 3-III 4-IV 5-V 6-VI	n (%)
B Medical Data					
Relevant medical diagnoses (ICD 11)			multi		Multiple answers possible
None		dm_0101	cat	0-no 1-yes	n (%)
Hypertension		dm_0102	cat	0-no 1-yes	n (%)
Dementia		dm_0103	cat	0-no 1-yes	n (%)
Renal failure		dm_0104	cat	0-no 1-yes	n (%)
Diabetes mellitus		dm_0105	cat	0-no 1-yes	n (%)
Heart arrhythmia		dm_0106	cat	0-no 1-yes	n (%)
Unknown		dm_0107	cat	0-no 1-yes	n (%)
Relevant medications			multi		Multiple answers possible

Characteristic	eCRF table	Variable name	Type	Scale	Comment/Analysis
None		dm_0111	cat	0-no 1-yes	n (%)
Antithrombotics		dm_0112	cat	0-no 1-yes	n (%)
Beta-adrenoreceptor antagonists		dm_0113	cat	0-no 1-yes	n (%)
Diuretics		dm_0114	cat	0-no 1-yes	n (%)

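### The per-protocol set selects on completion and on regular termination with at least seven days, so adherent participants stopped early after a 2A or 2B event leave it together with the event

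*Combined protocol and SAP*

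**What the plan says.** SAP 2.1, in the same words as Protocol 4.4, sets two conditions for the PP set. The first is "Participants that completed the study without major protocol deviations or violations"; the deviations listed are wrong or incorrect application, application missing for more than 72 hours, and "more than three missing study visits, inclusion/exclusion criteria not met". The second is that the participant "terminated the study regularly (study participation of at least 7 consecutive days". The study period is 14 days.

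The use of the set is stated in SAP 2.2: "An additional analysis of the primary efficacy variable in the PP analysis set will be used as sensitivity analysis". SAP 7.2 defines the event for that variable as the first GLOBIAD 2A or 2B and names Day 6 and Day 14 as the relevant timepoints.

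Protocol 2.3.2, item 6a, gives this as an example of a reason to discontinue: "Mycotic or bacterial inflammation, or other skin conditions in the study area that require topical (drug) treatment" with other products. Protocol 4.1.1 also lets the assessor end participation when a skin visit shows a condition judged incompatible with the study.

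The completion form in SAP 4.1 asks whether the subject completed regularly. One answer is "2-Yes, but before end of study visit on Day 14". The comment on the answer 'No' reads "Reasons for 0 might be withdrawal before randomization or screening failure".

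**The concern.** A PP set should be defined by eligibility and by how the product was applied. Completion and length of participation are neither, and here the outcome itself can shorten participation. Category 2B carries signs of clinical infection, which plausibly meets item 6a, so the event can lead to the stop and the stop to exclusion.

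Nothing in the documents keeps such a participant in. SAP 2.2 says that early leavers are analysed up to the time they leave, but that governs follow-up, not PP membership.

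The primary objective is to estimate incidence and effect sizes for a confirmatory trial, and SAP 2.2 calls the ITT and PP analyses both necessary for that planning. A PP incidence that has lost events would understate the event rate expected under good adherence.

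**Working it through.** **1. Two readings.** The seven-day text stands in brackets after 'regularly', so it can be read as the definition of regular termination (seven-day reading). If 'completed' means reaching Day 14, every earlier stop is excluded (strict reading). Three eligible, adherent participants:

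| Course | FAS | PP, seven-day reading | PP, strict reading |
|---|---|---|---|
| 2B found and stopped on Day 4 | in, event counted | out | out |
| 2B found and stopped on Day 10 | in, event counted | in, event counted | out |
| 2A found on Day 4, continues to Day 14 | in, event counted | in, event counted | in, event counted |

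The first row is the defect on either reading. The second shows that the terms do not settle membership.

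**2. The visit rule.** If visits after a stop count as missed, a participant last seen on Day 6 misses four (Days 8, 10, 12, 14) and is excluded by that rule as well. One last seen on Day 8 misses three and is not.

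**3. Day 6.** On elapsed days, PP membership needs participation beyond Day 6, so a PP contrast at Day 6 selects on status after the analysis time.

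**4. Size.** The plan has no figure to reproduce: it states no event rate, stop rate or dropout rate. The following inputs are assumptions: constant hazard over 14 days, true incidence p, and a share s of 2A/2B events stopped at the visit of detection. No one else is excluded.

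PP incidence = (p − r)/(1 − r), where r is the fraction of the arm removed.
- Strict reading: r = s·p.
- Seven-day reading: r = s·[1 − (1 − p)^(6/14)], i.e. events found by the Day 6 visit.

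Take control p = 20% and hazard ratio 0.5, so product p = 1 − 0.8^0.5 = 10.6%. The FAS then gives RR 0.53 and a risk difference of 9.4 points. With s = 50% in both arms:
- Strict: control (0.200 − 0.100)/(1 − 0.100) = 11.1%; product (0.106 − 0.053)/(1 − 0.053) = 5.6%. RR 0.50, risk difference 5.5 points, 50% of control events removed.
- Seven-day: control r = 0.5 × (1 − 0.8^(6/14)) = 0.5 × 0.091 = 0.046, so (0.200 − 0.046)/(1 − 0.046) = 16.2%; product 8.4%. RR 0.52, risk difference 7.8 points, 23% of control events removed.

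With 70 per arm there are 14 control events, of which 7 (strict) or about 3 (seven-day) are lost.

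Over control incidence 10–30% and s = 25–100%, equal in the arms, the share of control events removed is 25–100% (strict) or about 11–47% (seven-day). With s = 0, PP equals FAS.

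**5. Unequal stopping.** With no true effect and s = 50% in one arm and 25% in the other, the PP risk ratio runs from 0.68 to 1.46 (strict) or 0.89 to 1.13 (seven-day) over the same incidences.

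**The case against.** The strongest reply is that the text is milder than it looks. The bracket and the eCRF code for regular completion before Day 14 both support treating a stop from day 7 on as regular, so those participants and their events may stay. The comment on 'No' mentions only exits before randomisation, though just as possibilities. This stands, and it is why both readings are shown.

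The event is also not a stopping rule. Category 2A is not named in Protocol 2.3.2, and 1B is not a main-outcome event. A reader might infer that the whole PP set is conditioned on not failing. The documents do not support that: many participants with an event may continue to Day 14 and remain.

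A reader might further infer that PP cannot serve as a sensitivity analysis. That does not follow either. The planned measure is a hazard ratio, and when stops are equally common in the arms, relative measures hardly move: the RR above goes from 0.53 to 0.50 or 0.52. On the strict reading each arm's odds are multiplied by the same (1 − s), so the odds ratio does not change. Distortion of the ratio needs stop rates that differ by arm. That is possible but not documented. Separately, the 72-hour rule can exclude only participants in the two product arms, so PP exclusions can differ by arm by design.

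Safeguards exist. The FAS is primary and keeps these events, a complete-case analysis is planned, and reasons for PP exclusion are to be stated per group. These limit the consequence but leave the definition as it is.

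**Conclusion.** The point holds for one group. Eligible, adherent participants with a first 2A or 2B event who are stopped before seven days are removed from PP with the event on either reading. If 'completed' means Day 14, later stops go as well. The effect is to lower PP incidence and the risk difference in every arm where such stops occur, and to distort the ratio only if they differ by arm.

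The size cannot be derived from the documents; every figure above rests on assumed incidence, stop share and constant hazard, and is nil if no one is stopped after an event. The finding concerns a sensitivity analysis in an exploratory trial and leaves the primary result untouched. It should be corrected because the PP incidence is meant to inform the next trial and because two programmers could derive different sets from the present text. No view is taken on which stopping rule is right.

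**What to change.** In SAP 2.1:
1. Keep in PP every eligible participant without a major application deviation who had an IAD event before stopping, whatever the length of participation or reason for leaving, and count that event. The event is 2A/2B for the main analysis and any category for the no-initial-IAD analysis in SAP 7.3.
2. Keep eligible, adherent participants stopped early without an event in the same way, censored at the stop in the time-to-event analysis. Otherwise some participants with short follow-up would be in only because they had an event, and incidence would be biased upward.
3. Do not let the seven-day requirement exclude either group, including from a Day 6 contrast. Judge missed visits and missed applications only up to the stop.
4. Define 'completed' and 'terminated regularly' once, say how the seven days are counted, and reconcile both terms with the eCRF code for regular completion before Day 14.
5. Extend the promised table of PP exclusions to show, by arm, IAD status at the stop.

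Replacing the PP set by censoring at the first application deviation is not required. It is a trade-off, because censoring for missed applications would fall on the product arms only.

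The cost is SAP wording and one re-derived flag from skin, visit, diary and completion data already collected. Protocol 4.4 carries the same definition and recruitment is reported as finished (n = 220), so the SAP should record the departure and its reason. No stopping rule changes.

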2.2 Application

The primary efficacy analysis will be done using the FAS including estimated values from multiple imputations for missing values (ITT framework). Participants that die, discontinue participation or leave the institution during the study period will be analyzed until that time point (early termination).

An additional analysis of the primary efficacy variable in the PP analysis set will be used as sensitivity analysis. The safety analysis includes calculation of frequencies and rates of adverse and serious adverse events in the safety analysis set.

As the ITT analysis is intended to preserve the original randomization and to avoid potential bias due to exclusion, the PP analysis aims to analyze the possible effects of the intervention administered under optimal conditions. Therefore, both analyzes are a necessary component to determine the feasibility of the applied procedures as well as possible effects of the intervention. Especially with regard to planning of a subsequent confirmatory trial

[figure not shown]
3 Trial centres

The study was conducted in geriatric hospitals/geriatric wards (acute care setting) of participating hospitals and in institutional long-term care facilities (nursing home setting) of the federal state of Berlin, Germany with a recruitment of n = 220 patients. Of these, 25 subjects were enrolled from acute care settings (14 EGZB; 11 Charité-ITS) and 195 subjects were recruited across 18 different nursing homes.

Nr	Participating ward	Number of patients (n)
Geriatric hospitals		
1	EGZB	14
2	Charité intern ITS	11
Nursing homes		
1	NH-01	11
2	NH-02	19
3	NH-03	5
4	NH-04	19
5	NH-05	17
6	NH-06	10
7	NH-07	6
8	NH-08	9
9	NH-09	7
10	NH-10	19
11	NH-11	4
12	NH-12	25
13	NH-13	8
14	NH-14	7
15	NH-15	3
16	NH-16	3
17	NH-17	13
18	NH-18	10

3.1 Recruitment

All study procedures will be performed at the Charité.

4 Analysis variables

According to study protocol version 1.1, 15th June 2022, the following table presents the collected variables (first column). In total, eight study visits are planned. After inclusion, residents will be followed-up for 14 days.

Table 3: Study schedule for individual participants.

	Days															
	Enrollment	Allocation	Post-allocation													Close-out
Timepoint	-5 to 0	0	1	2	3	4	5	6	7	8	9	10	11	12	13	14
Formal requirements and allocation																
Eligibility screening	x															
Informed consent	x															
Randomization and allocation		x														
Participant characteristics																
Demographic variables (e.g. age, sex, care level)		x														
Relevant medical diseases		x														
Relevant medications		x														
Physical function (Barthel-Index)		x														
Cognitive status (MMSE)		x														
Incontinence characteristics		x														
Clinical skin assessment																
Gent Global IAD categorization (GLOBIAD)		x		x		x		x		x		x		x		x
Erythema (visual inspection)		x		x		x		x		x		x		x		x
Erythema (instrumental measurement)		x		x		x		x		x		x		x		x
Erosion		x		x		x		x		x		x		x		x
Maceration		x		x		x		x		x		x		x		x
IAD-related pain (NRS or PAINAD-G)		x		x		x		x		x		x		x		x
IAD-related itch		x		x		x		x		x		x		x		x
Patient satisfaction (NRS)		x		x		x		x		x		x		x		x
(Serious) Adverse Events or Incidents		x		x		x		x		x		x		x		x
Interventions and study-related procedures																
Study arm 1: Conduction of the standardized skin cleansing regime and application of the film-forming skin protectant																
Study arm 2: Conduction of the standardized skin cleansing regime and application of the hydrophobic skin protectant																
Study arm 3: Conduction of the standardized skin cleansing regime, no additional skin protectant																
Other																
Skin care diary completed by nurses																

4.1 Demography and baseline characteristics

Demographic information (e. g. age, sex, care level), incontinence type according to medical records, medical information (e. g. relevant main medical diagnoses and relevant regular medication) and further care specific data is collected for all participants.

Characteristic	eCRF table	Variable name	Type	Scale	Comment/Analysis
Patient-ID		mnpaid			
Visit Number		mnpvismo			
	mnppid_random				Randomization information (strata)
arm		rd_0050	cat	1-A 2-B 3-C	Blinded (label permuted)
	mnppid_visit				Visit information
Visit performed?		visit_0011	Cat.		
Date of visit		visit_0012	Date		
Reason for no visit		visit_0013	Char.		
Setting		sc_0020	Cat.	1-Nursing home (NH) 2-Geriatric Hospital (GH)	Important: mnppid_visit; not mnppid_screening! =>rename setting_sc_0020
	mnppid_completion				
Date of study termination		sc_0010	Date		For “time under study” Take diff(sc_0010,visit_0012==Day0)
Did the subject complete the study regularly?		sc_0021	cat	1-Yes, completion of end of study visit on Day 14 2-Yes, but before end of study visit on Day 14 0-No	Reasons for 0 might be withdrawal before randomization or screening failure
Reasons for early termination		Sc_0031 to Sc_0038			Consider sc_003x_txt Except for 0031,0032,0037

Characteristic	eCRF table	Variable name	Type	Scale	Comment/Analysis
	mnppid_demo				Demography & Medical Data
A Demography					
Age		dm_0020	Cont.	years	Mean (sd)
Sex		dm_0030	cat	1-male 2-female	n (%)
Body height		dm_0041	Cont.	cm	Mean (sd)
Body weight		dm_0051	Cont.	kg	Mean (sd)
BMI		dm_0060	cont	Score	Mean (sd)
Care level		dm_0070	cat	0-none 1-1 2-2 3-3 4-4 5-5 -1-Unknown	n (%)
Smoking status		dm_0080	cat	1-Smoker 2-Non-Smoker -1-Unknown	n (%)
Skin type		dm_0090	cat	1-I 2-II 3-III 4-IV 5-V 6-VI	n (%)
B Medical Data					
Relevant medical diagnoses (ICD 11)			multi		Multiple answers possible
None		dm_0101	cat	0-no 1-yes	n (%)
Hypertension		dm_0102	cat	0-no 1-yes	n (%)
Dementia		dm_0103	cat	0-no 1-yes	n (%)
Renal failure		dm_0104	cat	0-no 1-yes	n (%)
Diabetes mellitus		dm_0105	cat	0-no 1-yes	n (%)
Heart arrhythmia		dm_0106	cat	0-no 1-yes	n (%)
Unknown		dm_0107	cat	0-no 1-yes	n (%)
Relevant medications			multi		Multiple answers possible

Characteristic	eCRF table	Variable name	Type	Scale	Comment/Analysis
None		dm_0111	cat	0-no 1-yes	n (%)
Antithrombotics		dm_0112	cat	0-no 1-yes	n (%)
Beta-adrenoreceptor antagonists		dm_0113	cat	0-no 1-yes	n (%)
Diuretics		dm_0114	cat	0-no 1-yes	n (%)
Medication influencing the renin angiotensin		dm_0115	cat	0-no 1-yes	n (%)
Psychoanaleptics		dm_0116	cat	0-no 1-yes	n (%)
Antibiotics		dm_0117	cat	0-no 1-yes	n (%)
Unknown		dm_0118	cat	0-no 1-yes	n (%)
Diarrhoea		dm_0120	cat	1-Yes 0-No -1-Unknown	n (%)
Urinary tract infection		dm_0130	cat	1-Yes 0-No -1-Unknown	n (%)

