4.2 Outcome variables

Because of the exploratory nature of the trial and according to methodological guidance for exploratory trials, a distinction between primary and secondary endpoints is not made [23]. The presence of IAD is, however, with consideration of the study protocol considered as main outcome variable, i.e. primary outcome.

Variables marked with (day0) will be considered as baseline data. All outcome variables are measured in eight study visits in total (one baseline visit [Day0] and seven follow-up visits [Day2, Day4, ..., Day14]).

Characteristic	eCRF table	Variable name	Type	Scale	Comment/Analysis
IAD incidence	mnppid_skin				Main outcome Measured via occurrence of IAD at given visit (skin_0011)
IAD present?		skin_0011	cat	0-no 1-yes	n (%)
Location front		skin_0015	cat	0-no 1-yes	n (%)
Location back		skin_0016	cat	0-no 1-yes	n (%)
GLOBIAD category (front)		skin_0012	cat	1-1A 2-1B 3-2A 4-2B	n (%) (check skin_0015)
GLOBIAD category (back)		skin_0017	cat	1-1A 2-1B 3-2A 4-2B	n (%) (check skin_0016)
Erythema (visual)					Multi variable
"Redness?"		skin_0021		0-None 1-Pink 2-Red/bright red	main focus if available, else build variable based on 0026, 0027a and 0028a; (highest level counts) n (%)
n.a.		skin_0023		0-no 1-yes	Check if contradicts skin_0026, 0027a and 0028a
None		skin_0026		0-no 1-yes	
Pink		skin_0027a		0-no 1-yes	
Front		skin_0027b		0-no 1-yes	n (%)
Back		skin_0027c		0-no 1-yes	n (%)
Red/bright red		skin_0028a		0-no 1-yes	
Front		skin_0028b		0-no 1-yes	n (%)
Back		skin_0028c		0-no 1-yes	n (%)
Erythema level (1)		Func_0081 (day0) func_0141	Numeric	Arbitrary units (AU) from 0 (= no erythema) to 999 (= extreme erythema)	Mean (sd) check func_0082 func_0142, func_0143
Erythema level (2)		Func_0083 (day0) func_0144	Numeric	Arbitrary units (AU) from 0 (= no erythema) to 999 (= extreme erythema)	Mean (sd) check func_0084

Characteristic	eCRF table	Variable name	Type	Scale	Comment/Analysis
					func_0145, func_0146
Erythema level (total)			Numeric	Arbitrary units (AU) from 0 (= no erythema) to 999 (= extreme erythema)	Mean (sd) of (Erythema level 1 + Erythema level 2)/2
Erosion					
"Erosion present?"		skin_0041		0-no 1-yes	n (%)
Front		skin_0044		0-no 1-yes	n (%)
Back		skin_0045		0-no 1-yes	n (%)
Maceration					
"Maceration present?"		skin_0051		0-no 1-yes	n (%)
Front		skin_0054		0-no 1-yes	n (%)
Back		skin_0055		0-no 1-yes	n (%)
Local intolerances					
Have any local intolerances occurred since the last visit?		skin_0061		0-no 1-yes	n (%)

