5.1 Missing values

In all analyses, missing values on either the outcome measures or on the covariates will be handled by using multiple imputation by chained equation (MICE) with $m = 30$ imputed datasets if MAR or MCAR assumption holds. To evaluate whether individual missings are MAR, MCAR or MNAR we will use information on reasons of missings or drop out (e.g. if patients drop out due to worsening of health status or not). In case of death, no imputation will be implemented for the time afterwards.

6 Sample size

Due to the exploratory nature of the trial, a formal sample size calculation is not applicable [23]. The trial has two subgroup strata (I) sex (male/female); (II) condition of the skin (no IAD vs. IAD Category 1A) and three treatment arms. Based on these conditions and following the recommendations for exploratory trials [36], a sample size of $n = 60$ participants per treatment group is considered feasible and sufficient to describe group differences. In order to compensate a possible loss-to-follow-up, $n = 70$ patients per group will be included.

7 Statistical analyses / methods

For all analyses, appropriate descriptive statistics (mean, standard deviation, median, interquartile range, absolute and relative frequencies) depending on the scale and distribution of the outcome variable for each time point will be presented. For relative frequencies of outcome variables, their cumulative incidences will be reported as well. Sensitivity analyses include per protocol analyses and complete case analyses in the ITT (without imputation).

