7.2 Analyses of endpoints

Because of the exploratory nature of the trial and according to methodological guidance for exploratory trials, a distinction between primary and secondary endpoints is not made [23]. Because the main aim is to prevent IAD, IAD incidence is likely to be considered as a primary outcome in a possible subsequent confirmatory trial and is therefore considered as primary efficacy variable.

For all outcomes, total group differences are reported by the corresponding effect size based on the statistical models as outlines below and corresponding 95% confidence intervals. Relevant timepoints will be Day 6 and Day14. Day0 reports will be presented as is.

The relevant blinded group comparisons are: A vs. B; A vs. C; B vs. C.

For cumulative incidence rates of IAD, Kaplan-Meier Curves will be presented with time ranging from inclusion to IAD onset, i.e. the first occurrence of IAD 2A or 2B. Censoring occurs if patients withdraw from the study before the onset of an IAD or if the study is terminated before IAD onset. Mixed effects Cox regression model (shared frailty model) will be carried out for group comparisons of incidence rates. The latter includes group allocation, sex, setting (nursery home, geriatric hospital ward) and time (continuous) as fixed effects and random intercepts for the ward and the patients. The resulting Hazard ratios for IAD will be presented. Potential non-linear time effects will be explored and modelled using fractional polynomials or splines.

Group differences for categorical, dichotomous responses are calculated by estimating group effects from either generalized linear mixed-effects models (binary logistic) - including particular baseline status (maceration, IAD-related itch), group allocation, sex, setting and time as fixed effects and random intercepts per ward and patients - or nonparametric analysis of longitudinal data depending on the distribution of the data. For the Erosion model, no baseline adjustment is considered due to its presence is an exclusion criterion.

List:

- Erosion (no/ yes)
- Maceration (no/ yes)
- IAD related itch (no/ yes) [only measured if IAD present]
- IAD-related pain (no/yes) [only measured if IAD present]

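### Event-free participants are censored at withdrawal or termination, not at their last skin assessment, so missed visits before exit can count as IAD-free and understate incidence

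*Combined protocol and SAP*

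**What the plan says.** - **How IAD is observed.** SAP 4.2 gives the main outcome as "Measured via occurrence of IAD at given visit (skin_0011". The schedule is "one baseline visit [Day0] and seven follow-up visits [Day2, Day4, ..., Day14". SAP 7.2 takes the first GLOBIAD 2A or 2B as the event for the Kaplan-Meier curves.
- **When follow-up ends.** SAP 7.2: "Censoring occurs if patients withdraw from the study before the onset of an IAD or if the study is terminated before IAD onset". No variable is named for the censoring date. SAP 2.2 adds that participants who die, discontinue or leave "will be analyzed until that time point (early termination". Protocol 4.3 has the same censoring rule.
- **The follow-up time derived.** The SAP 4.1 entry for the date of study termination (sc_0010) carries the note "Take diff(sc_0010,visit_0012==Day0" for time under study. The only other mention of days under study is an optional denominator for diary adherence in SAP 4.4.3.
- **Missed visits.** Protocol 2.3.2 lists "More than three missing study visits" as a reason to discontinue, so three are tolerated and the fourth ends participation.
- **Missing data.** SAP 5.1: "missing values on either the outcome measures or on the covariates will be handled by using multiple imputation by chained equation (MICE", with 30 datasets, if MAR or MCAR holds. SAP 2.2 and 7.2.1 apply this to the primary efficacy analysis. SAP 7 also plans "complete case analyses in the ITT (without imputation" as a sensitivity analysis.

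Neither document censors at the last skin assessment, mentions interval censoring, or says how imputed visits enter the Kaplan-Meier or Cox data.

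**The concern.** A participant is known to be free of the event only up to the last visit at which the skin was assessed. Someone censored later stays in the denominator at visits where no assessment was made. The estimated hazard at those visits is diluted and cumulative incidence is too low.

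The main use of this trial is to supply effect sizes for a confirmatory trial (SAP 1.1.1). A uniform understatement would make the control incidence used for planning too low. If missed visits before exit are more common in one arm, the hazard ratio moves with no treatment effect. The protocol gives one reason why they might differ: the rule on more than 72 hours without product (2.3.2, criterion 8) applies only to the intervention groups. During an absence, a control could therefore remain in the study through more missed visits than a participant in a protectant arm.

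**Working it through.** **1. Visits.** 1 + 14/2 = 8, which agrees with the eight visits in SAP 4 and 4.2.

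**2. Longest unobserved stretch.** All 2^7 = 128 patterns of missed post-baseline visits were enumerated, with discontinuation dated on the fourth missed visit.
- Discontinued participants: at most 8 trailing days, only with four consecutive misses (for example last seen Day 6, terminated Day 14: 14 − 6 = 8).
- Within the three allowed misses: at most 6 trailing days (last seen Day 8: 14 − 8 = 6).
- Three misses between two performed visits: a gap of 4 × 2 = 8 days, closed by an actual assessment.

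**3. Loss.** The plan allocates 70 per arm and analyses 60, so the allowance is 10/70 = 14.3%.

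**4. Expected Kaplan-Meier estimate at Day 14.** The documents give no IAD incidence for this trial, so true values p of 5%, 10%, 20% and 35% are assumed, with a constant hazard per visit:

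h = 1 − (1 − p)^(1/7)

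At each visit let O be the participants still event-free and assessed. Let U be those with no further assessment whose termination date has not yet passed. Expected events are hO and the risk set is O + U, so

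estimate = 1 − ∏ [1 − hO/(O + U)].

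Example: p = 20% gives h = 0.03137. Ten of 70 are lost, with last assessments spread evenly over Days 0, 2, 4 and 6 and termination 8 days later.

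| Day | O | U | hO/(O+U) | Survival |
|---|---|---|---|---|
| 2 | 67.50 | 2.50 | 0.0303 | 0.970 |
| 4 | 62.96 | 4.92 | 0.0291 | 0.942 |
| 6 | 58.64 | 7.27 | 0.0279 | 0.915 |
| 8 | 54.53 | 9.54 | 0.0267 | 0.891 |
| 10 | 52.82 | 7.04 | 0.0277 | 0.866 |
| 12 | 51.16 | 4.62 | 0.0288 | 0.841 |
| 14 | 49.55 | 2.27 | 0.0300 | 0.816 |

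The estimate is 1 − 0.816 = 18.4% against a true 20%.

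All scenarios with 10 of 70 lost (for the first two rows, last assessments are spread over Days 0 to 12):

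| Censoring date | 5% | 10% | 20% | 35% |
|---|---|---|---|---|
| Termination before the next scheduled visit | 5.0 | 10.0 | 20.0 | 35.0 |
| Termination on the next, unperformed visit (2 days) | 4.9 | 9.8 | 19.6 | 34.4 |
| Every loss with the 8-day gap | 4.6 | 9.2 | 18.4 | 32.3 |
| Last performed assessment | 5.0 | 10.0 | 20.0 | 35.0 |

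The understatement is 0.1 to 0.6 points for 2-day gaps and 0.4 to 2.7 points for 8-day gaps. With 20 of 70 lost, all at 8 days, the estimates would be 4.2, 8.3, 16.7 and 29.5%.

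**5. Hazard ratio when the true value is 1.0 (p = 20%).**
- Protectant arm with 2-day gaps, control with 8-day gaps: ln(0.804)/ln(0.816) = 1.07.
- One arm with 8-day gaps, the other with none: ln(0.816)/ln(0.800) = 0.91.

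Both assume that every loss in an arm follows the stated pattern.

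**The case against.** The strongest reply has four parts.

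**The SAP 4.1 line is not the survival time.** It is a derivation note in the section on demography and baseline characteristics, and SAP 7.2 names no censoring variable. A reader might infer that the SAP prescribes sc_0010 for the Kaplan-Meier analysis. The documents do not say so; it is an inference. It is a strong one, because censoring is tied to withdrawal or termination and no other end of follow-up is derived.

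**The primary analysis is imputed.** Missed visits are identifiable in the data, and under multiple imputation they need not count as IAD-free. This stands as far as it goes. But imputation depends on MAR or MCAR, its link to the time-to-event data is not described, and the complete-case sensitivity analysis has none.

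**Long gaps may be rare.** The study team visits on site, and reviews diaries at least every second day (protocol 2.5). A reader might take 8 of 14 unobserved days as typical. It is a maximum that needs four consecutive missed visits, and such participants are already outside the per-protocol set. Nor do the documents say that sc_0010 is dated to Day 14 for someone last seen on Day 6. The 6-day case, however, breaches no missed-visit limit, so that limit does not keep it out of the per-protocol set.

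**The effect is small against sampling error.** At 20% and n = 70, the standard error of an incidence is √(0.2 × 0.8/70) = 4.8 points, against a shift of 1.6 points with all losses at 8 days. That is correct and limits the weight of the point. It does not justify keeping an avoidable bias of known direction.

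**Conclusion.** The point holds as a conditional one. Incidence can be understated when the termination date reaches or passes one or more unperformed visits that are not imputed. Ordinary withdrawal between on-schedule visits gives no Kaplan-Meier bias. A reader might conclude that incidence is biased downward in every arm, or that a hazard ratio near 0.91 should be expected under no effect. The documents support neither: both need gap patterns that nothing in them establishes.

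The sizes in the working rest on assumed incidences, a constant hazard, visits on the scheduled days, and a loss equal to the planned allowance. Within those limits, the 8-day figures are the upper end for 10 of 70 lost. Censoring at the last performed assessment returns the true value in every scenario computed. The change is worth making because the estimates are meant to inform a later trial and the current rule leaves the censoring date to the analyst.

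**What to change.** In SAP 7.2, with a matching note in 4.1:

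1. Censor event-free participants in the Kaplan-Meier and Cox analyses at the date of their last performed skin assessment, meaning the last visit with non-missing skin_0011 and, where IAD is present, a GLOBIAD category. Keep sc_0010 for describing retention and days under study.
2. Apply this rule in the complete-case analysis and any other analysis without imputation.
3. For the imputed primary analysis, state that a missed visit enters the time-to-event data only through its imputed status and is never IAD-free by default. Without this statement, rule 1 would conflict with the imputation in SAP 2.2 and 7.2.1.

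The cost is one derived variable from data already held (visit_0011, visit_0012, skin_0011 and the GLOBIAD fields), a few lines of text, and slightly less follow-up time counted. The rule does not address late detection when missed visits are followed by a performed one; an interval-censored analysis would cover that if such gaps prove common.
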